4.5.3. Medical History

Medical history will be summarized by System Organ Class and Preferred Term using the Medical Dictionary for Regulatory Activities (MedDRA), by treatment group and overall.

Medical history is summarized by subject incidence rates; therefore, a subject contributes only once to the count for a given medical history (SOC or preferred term).

Medical history will be reported in a listing.

4.5.4. Endometriosis History

Time since first medical diagnosis/treatment, first surgical diagnosis and most recent surgical diagnosis in years defined as (randomization date – date of diagnosis)/365.25 will be summarized.

Presence within 2 months before screening and ongoing symptoms of the following symptoms will be summarized, by treatment group and overall: Dyspareunia, Dyschezia, Dysuria, Adenomyosis, Rectovaginal endometriosis nodes.

Endometriosis History will be reported in a listing.

4.6. Efficacy Evaluation

Efficacy analysis will be conducted using the Full Analysis Set. Primary and ranked secondary analyses will be repeated on the Per Protocol Set.

4.6.1. Meaningful Change Threshold Estimation

The analyses to estimate the meaningful change thresholds (MCTs) using the blinded interim data will be produced by an independent programming team and statistician to the Sponsor. Analysis datasets will be provided by Cytel. The external programming team will execute the analyses and the statistician will review and interpret the results and provide recommendations to the Sponsor for threshold estimation. Analyses to determine the MCTs will be described in a separate document.

While the responder threshold analyses using these MCTs (see Section 4.6.2) will be conducted on all FAS subjects, the derivation of the MCTs for the co-primary endpoints was undertaken once patients had completed Month 3, using data up to Month 3 on the Threshold Analysis Set (FAS subjects with available anchor data). The derivation of the MCTs for the additional supportive responder analyses on the ranked secondary endpoints will be undertaken once patients have completed Month 6, using data up to Month 6 on the M6 Threshold Analysis Set (FAS subjects with available anchor data at Month 6). For the specific mPGIS anchors, all subjects enrolled after Protocol Amendment V3.0 and collecting data using updated

Sponsor:	ObsEva		
Protocol:	18-OBE2109-003		
Document Version No.:	V5.0	Document Date:	13-JUN-2022

e-Diary (expected to be approximately 50 subjects) with available anchor data at Baseline and Month 3 (Month 6 for additional supportive responder analyses on the ranked secondary endpoints) are considered, as these specific mPGIS anchors were introduced as part of Amendment 3. For the generic mPGIS and PGIC anchors the analyses were (will be) performed on a random sample of 200 subjects with data for both anchors: mPGIS at Baseline and Month 3 (respectively Month 6 for ranked secondary endpoints) and mPGIC at Month 3 (respectively Month 6). The same random sample was (will be) used for PGIS and PGIC anchors. For the EHP-30 Pain Domain endpoint, the analyses will be repeated to confirm results using the remaining subjects (out of the selected sample of 200 subjects) from the study. As with the under treatment efficacy analysis, for subjects who discontinue treatment prior to Month 3 (prior to Month 6 for ranked secondary endpoints), the 28 calendar days immediately prior to and including the last dose date will be used, along with the closest time-matched monthly anchor measures.

SAS Code for Random Sample:

proc surveyselect data=dataset out=sample method=srs sampsize=200 seed=12345;

run;

4.6.1.1. Responder Threshold Analysis

Responder threshold analyses will be performed for the co-primary endpoints (See Section 4.6.2) and, as additional supportive analyses for the ranked secondary endpoints (see Sections 4.6.3.1 to 4.6.3.5) using the MCTs estimated from the blinded data.

The final responder thresholds will be included in the final SAP prior to breaking the blind to the sponsor and main study team after Month 6. Based on the results from the Phase 2b Edelweiss study, it is expected that the responder threshold will be in the range of a 0.7 to 1.25 point reduction in pain in the 4-point VRS for a 2-point improvement in anchor status and a 0.25 to 0.75 point reduction in pain in the 4-point VRS for a 1-point improvement in anchor status. The numerical thresholds for DYS are expected to be larger than those for NMPP. No MCTs were estimated in Phase 2 for the other Phase 3 ranked secondary endpoints (overall pelvic pain, dyschezia, dyspareunia, EHP-30 pain domain). In Phase 3, additional anchor measures are included to estimate MCTs for these endpoints.

4.6.1.1.1. Primary Efficacy Endpoints

The two co-primary, composite, efficacy endpoints are reaching the responder threshold in 1) DYS and 2) NMPP while having no accompanying increase in analgesics for EAP. These endpoints will be assessed at Month 3.

For each of the co-primary endpoints, the criterion for defining a subject as a responder over the last 28 days of randomized treatment up to the Month 3 visit will be a reduction of X (the MCT) or greater from baseline in pain. The threshold for response in the responder analysis (i.e., the value of X) will be chosen to represent a clinically meaningful reduction in pain and may not be the same for each endpoint (DYS

Sponsor:	ObsEva		
Protocol:	18-OBE2109-003		
Document Version No.:	V5.0	Document Date:	13-JUN-2022

and NMPP). The obtained recommended values of X following meaningful change threshold estimation at Month 3 is reported in Section 4.6.1.3.

4.6.1.1.2. Ranked Secondary Endpoints

The six ranked secondary efficacy endpoints for which additional supportive responder analyses will be performed are reaching the MCT in 1) DYS, 2) NMPP, 3) dyschezia, 4) overall pelvic pain, 5) EHP-30 Pain domain, and 6) dyspareunia. These endpoints will be assessed at Month 6.

For each of the additional supportive responder analyses for the ranked secondary efficacy endpoints, the criterion for defining a subject as a responder over the last 28 days of randomized treatment up to the Month 6 visit will be a reduction of X (the MCT) or greater from baseline. The threshold for response in the responder analysis (i.e., the value of X) will be chosen using data at Month 6, to represent a clinically meaningful reduction and may not be the same for each endpoint (DYS, NMPP, dyschezia, overall pelvic pain, EHP-30 Pain domain, dyspareunia). The MCT of DYS and NMPP may be different than those obtained at the Month 3 MCT analysis. The obtained recommended values of X following meaningful change threshold estimation at Month 6 is reported in Section 4.6.1.4.

4.6.1.2. Estimation of Meaningful Change Threshold

Anchor-based methods will be used to estimate the MCT for each co-primary and ranked secondary efficacy endpoint. Anchor-based methods are where an external criterion (anchor) is used to provide an indication of the minimal change in the PRO that is of (clinical) relevance. The anchor-based methods will include estimation of mean within-group change, with 95% confidence intervals (CIs), and receiver operating characteristic (ROC) curves to identify specific cut points. The MCT determination will also consider supportive information from cumulative distribution function (CDF) and probability distribution function (PDF) curves. Lastly, shift tables will be used, where appropriate, to examine the change in the endpoint by baseline and Month 3 (respectively Month 6 for ranked secondary endpoints) anchor score.

Because linzagolix is expected to improve the symptoms of endometriosis, the MCT for each endpoint will indicate the amount of *improvement* in each endpoint which is perceived to indicate a meaningful change. The analyses will be conducted using blinded data from Edelweiss 3 that combine the data from all treatment arms including the Placebo arm and use change from Baseline to Month 3 for the co-primary endpoints and change from Baseline to Month 6 for the ranked secondary endpoints.

Anchor-based methods are the preferred methods for estimating MCTs. An anchor is a reference measure that is used to determine change. The purpose of an anchor measure is to identify change on the target clinical outcome assessment (COA) measure that represents patient (or clinician) perceived improvement or deterioration. Any potential anchor should be less complex than the measure it is being used to assess. Anchors are expected to have a correlation coefficient of \geq 0.35 with the target COA measure to be used in the anchor-based analysis (Revicki et al. 2008). Correlation coefficients for Baseline scores and change from Baseline scores will be assessed to inform the suitability of the proposed anchor.

Sponsor:	ObsEva		
Protocol:	18-OBE2109-003		
Document Version No.:	V5.0	Document Date:	13-JUN-2022

Potential anchor measures

The following single-item measures were selected to be evaluated as possible anchors for the two coprimary endpoints DYS and NMPP: monthly patient global impression of severity (mPGIS) items of DYS and NMPP, together with the non-specific mPGIS and patient global impression of change (PGIC) items of endometrial symptom severity (Table 5). The following single-item measures were selected to be evaluated as possible anchors for the ranked secondary efficacy endpoints (DYS, NMPP, dyschezia, overall pelvic pain, EHP-30 Pain domain, dyspareunia): mPGIS items of DYS, NMPP, dyschezia, overall pelvic pain, difficulty in daily activities, and dyspareunia, together with the non-specific mPGIS and patient global impression of change (PGIC) items of endometriosis symptom severity (Table 5).

Sponsor:	ObsEva		
Protocol:	18-OBE2109-003		
Document Version No.:	V5.0	Document Date:	13-JUN-2022

Table 5 Proposed anchors for MCT estimation for each endpoint

DYS	NMPP	Overall Pelvic	Dyschezia	EHP-30 Pain	Dyspareunia		
		Pain		domain			
Endpoint (shaded = main study endpoints)							
Daily 0-3 VRS	Daily 0-3 VRS	Daily 0-10 NRS	Daily 0-10 NRS	Monthly 0-100	Daily 0-3 VRS		
0 – No pain	0 – No pain	0 (No pelvic	0 (No dyschezia	EHP-30 Pain	0 - No pain during sexual intercourse.		
1 – Mild	1 – Mild	pain) to 10	pain) to 10	Domain score	1 - I was able to tolerate the pain during sexual intercourse.		
2 – Moderate	2 – Moderate	(Worst pain)	(Worst pain)		2 - Intercourse was interrupted due to pain.		
3 - Severe	3 - Severe	NRS	NRS		3 - I avoided sexual intercourse because of anticipation of pain		
Bleeding days	Non-Bl days	All days	All days	4-week recall	All days		
Monthly anchors					·		
a) Specific anch	nors						
mPGIS 0-4 VRS	mPGIS 0-4 VRS	mPGIS 0-4 VRS	mPGIS 0-4 VRS	mPGIS 0-4 VRS	mPGIS 0-4 VRS		
menstrual PP	non-menstrual PP	Overall PP	Dyschezia	Difficulty activities	Dyspareunia		
0 – No pain	0 – No pain	0 – No pain	0 – No pain	0 – No difficulty	0 – No symptoms		
1 - Very Mild	1 - Very Mild	1 - Very Mild	1 - Very Mild	1 – Slight	1 - Tolerated discomfort during intercourse		
2 – Mild	2 – Mild	2 – Mild	2 – Mild	2 – Mild	2 - Interference of usual frequency of sexual intercourse due		
					to pain		
3 – Moderate	3 – Moderate	3 – Moderate	3 – Moderate	3 – Moderate	3 – Avoids, or wishes to avoid, intercourse because of pain		
4 - Severe	4 - Severe	4 - Severe	4 - Severe	4 - Severe			
b) Generic anch	nors						
			mPGIS 0-4 VRS	Endometriosis sympto	oms		
0 – No pain							

CRS-BS-TP-000005 V 1.0

Page 57 of 127

Sponsor:	ObsEva		
Protocol:	18-OBE2109-00	3	
Document Version No.:	V5.0	Document Date:	13-JUN-2022

1 - Very Mild				
2 – Mild				
3 – Moderate				
4 - Severe				
PGIC 7-pt VRS Endometriosis Symptoms				
-3 - Very much improved				
-2 - Much improved				
-1 - Minimally improved				
0 - No change				
1 - Minimally worse				
2 - Much worse				
3 - Very much worse				

CRS-BS-TP-000005 V 1.0

Page **58** of **127**

Cytel Confidential: This is a controlled document and shall not be changed, saved, copied or reproduced by any unauthorized person.

Sponsor:	ObsEva		
Protocol:	18-OBE2109-003		
Document Version No.:	V5.0 Document Date: 13-JUN-2022		

4.6.1.3. Results of Meaningful Change Threshold Analysis for the Co-Primary Endpoints

Following the Meaningful Change Threshold analysis performed on soft locked data at Month 3, the recommendation for the final MCT estimates of the co-primary endpoints is the following:

- Dysmenorrhea (VRS): X=-1.10
- Non-Menstrual Pelvic Pain (VRS): X=-0.80

The criterion for defining a subject as a responder over the last 28 days of randomized treatment up to Month 3 will be a reduction of 1.10 or greater from baseline pain for Dysmenorrhea; a reduction of 0.80 or greater from baseline pain for Non-Menstrual Pelvic Pain.

4.6.1.4. Results of Meaningful Change Threshold Analysis for the Ranked Secondary Endpoints

Following the Meaningful Change Threshold analysis performed on Month 6 database lock, the recommendation for the final MCT estimates of the ranked secondary endpoints are the following:

- Dysmenorrhea (VRS): X=-1.25
- Non-Menstrual Pelvic Pain (VRS): X=-0.85
- Dyschezia (Numeric Rating Scale NRS): X=-1.5
- Overall pelvic pain (NRS): X=-2.7
- EHP-30 pain domain: X=-28
- Dyspareunia (VRS): X=-0.9

The criterion for defining a subject as a responder over the last 28 days of randomized treatment up to Month 6 will be a reduction of 1.25 or greater from baseline pain for Dysmenorrhea; a reduction of 0.85 or greater from baseline pain for Non-Menstrual Pelvic Pain; a reduction of 1.5 or greater from baseline pain for Dyschezia; a reduction of 2.7 or greater from baseline pain for Overall Pelvic Pain; a reduction of 0.9 or greater from baseline pain for Dyspareunia.

The criterion for defining a subject as a responder at Month 6 or discontinuation will be a reduction of 28 or greater from baseline for EHP-30 pain.

Sponsor:	ObsEva		
Protocol:	18-OBE2109-003		
Document Version No.:	V5.0	Document Date:	13-JUN-2022

4.6.2. **Primary Efficacy Endpoint**

4.6.2.1. Primary Efficacy Analysis

4.6.2.1.1. Primary Endpoint Specifications

The primary efficacy analysis aims to estimate the effect of linzagolix versus placebo on DYS and NMPP over the last 28 days up to and including the Month 3 visit or, for subjects who discontinued randomized treatment prior to the Month 3 visit, over the last 28 days of randomized treatment. Use of analgesic medication for EAP will be included in the responder definitions. A responder for each of the co-primary endpoints needs to demonstrate both a reduction in pain (DYS or NMPP, depending on the endpoint) and a stable or decreased use of analgesics for EAP (assessed separately for DYS and NMPP). Any subject who does not meet both of these criteria will be defined as a non-responder.

As detailed below, in line with ICH E9 (R1) addendum: four attributes (population, endpoint, treatment and population level summary) have been specified to translate the primary objective into treatment effect that is to be estimated (estimands):

- A. Population: Premenopausal women aged 18 to 49 years inclusive at screening, with surgically and, if available, histologically confirmed pelvic endometriosis and with moderate to severe EAP.
- B. Endpoint: The two co-primary, composite efficacy endpoints are clinically meaningful reduction from baseline to the last 28 days on randomized treatment, preceding the Month 3 visit or discontinuation, along with a stable or decreased use of analgesics for EAP, in the mean daily assessment of 1) DYS and of 2) NMPP measured on a Verbal Rating Scale (VRS) using an electronic diary.
- C. Treatment: linzagolix administered orally once daily for up to 3 months at a dose of 75 mg alone or of 200 mg in combination with ABT, versus placebo
- D. Population-level summary: Odds-ratio of proportions of responders of linzagolix versus placebo from a logistic regression model for each co-primary endpoint, with treatment group as the main effect (three values) and including the baseline pain score as a covariate.

Intercurrent events: Increased use of EAP analgesia is a non-response in the endpoint definition. Treatment discontinuations are assessed up to the time of discontinuation. Randomized treatment will be considered, regardless of lack of compliance to treatment or treatment assignment errors. The clinical question of interest is based on a while-on-treatment strategy for discontinuation and composite strategy for analgesic use. Lack of compliance to treatment and treatment assignment errors are handled using a treatment policy strategy.

The "while-on-treatment strategy" was chosen for the intercurrent event of discontinuation of treatment for the co-primary endpoints based on the recommended strategies for addressing intercurrent events in the (then draft) ICH E9 (R1) guideline.

Sponsor:	ObsEva	ObsEva		
Protocol:	18-OBE2109-00	18-OBE2109-003		
Document Version No.:	V5.0 Document Date: 13-JUN-2022			

The response to treatment prior to the occurrence of the patient discontinuing treatment is of clinical interest for a symptomatic treatment of endometriosis-associated pain. Patients and prescribers are generally interested in what happens when a patient actually takes (and can take) the treatment. This corresponds most directly to the "while on treatment" strategy for treatment discontinuation. Of note, a comparison of patient disposition and discontinuation rates will also constitute an important aspect when interpreting the study results. In addition, a "while-on-treatment" strategy for efficacy aligns with the analysis of adverse events, which are also considered while on treatment. Moreover, as endometriosis-related pelvic pain is measured repeatedly each day, the variable can be readily calculated for the 28-day period up to the point of discontinuation and the value up to the time of discontinuation can be considered to account for the intercurrent event.

For each of the co-primary endpoints, the criterion for defining a subject as a responder over the last 28 days of randomized treatment up to the Month 3 visit will include a reduction of X or greater from baseline in pain, where X was determined by a meaningful change threshold estimation using appropriate anchors as described in Section 4.6.1, as well as stable or decreased use of analgesics for EAP. Results of the meaningful change threshold estimation 4.6.1.3.

Mean pelvic pain scores for DYS and for NMPP will be calculated by averaging over the corresponding 28 calendar days immediately prior to and including the day of the Month 3 visit. DYS will use days with uterine bleeding, defined as those days on which the subject records any uterine bleeding or spotting in the subject eDiary; NMPP will use days with no uterine bleeding. If a subject's mean score for DYS is undefined numerically because her daily eDiary reports indicate that she did not experience uterine bleeding on any days during the 28 calendar day period, then the mean score for DYS will be set equal to zero (which reflects the absence of any DYS during that reporting time period). Similarly, if a subject's diary reports indicate that she only experienced days with uterine bleeding during the period, then the mean score for NMPP will be set equal to zero. For subjects who discontinue treatment prior to Month 3, the last available observations prior to discontinuation will be used, in order to estimate the treatment effect while under treatment, that is the 28 calendar days immediately prior to and including the last dose date. The baseline mean overall pelvic pain scores for DYS and NMPP will be calculated by averaging over the two baseline menstrual cycles (as defined in section 4.2.10), which may not be exactly 28 days each. For both DYS and NMPP, responses of "None," "Mild," "Moderate," and "Severe" will be assigned a score of 0, 1, 2, and 3, respectively.

For the assessment of stable or decreased use of analgesics for EAP (assessed separately for DYS and NMPP), the analgesic use for any defined period will be based on the mean of the total pill count for each class of rescue analgesics (endometriosis-associated). The total pill count for each class of rescue analgesic is the sum of the pill count of the corresponding class of rescue analgesic, as reported in the eDiary during the time period of interest. Baseline analgesic use will be calculated as the mean of the daily pill count of analgesics over the two baseline menstrual cycles (as defined in section 4.5.2). For the purposes of determining a stable or decreased use of analgesics, the averaging will be done over the same calendar days as used for the pelvic pain scores (i.e. for DYS days with uterine bleeding, defined as

Sponsor:	ObsEva		
Protocol:	18-OBE2109-003		
Document Version No.:	V5.0	Document Date:	13-JUN-2022

those days on which the subject records any uterine bleeding or spotting in the subject eDiary; for NMPP days with no uterine bleeding). The evaluation of stable or decreased use of analgesics will be done per the specification in 7.1 Appendix A.

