Subjects whose response cannot be assessed for the co-primary efficacy endpoints, e.g. due to lack of on treatment pain data (i.e. subjects who received less than 28 days of treatment), will be considered as non-responders. In addition, for outputs presenting the numeric change from baseline, such subject will be assigned a change from baseline of zero. It is expected that very few subjects will be affected by these rules.

There may be missing data during the screening period and whilst under treatment, for example, missed days of completing the eDiary. The primary analyses will use observed data only in such cases, provided that a minimum number of completed daily eDiary entries are available. This effectively assumes that the individual values such as daily eDiary assessments (observed or not) are independent of being missing. Subjects who have less than the minimum number of days available will be excluded from the analysis. This is valid under the assumption that such data is MAR, conditional on the baseline value.

The required minimum number of completed daily eDiary entries will be set to 12 days of each 28-day period (two Baseline menstrual cycles and the 28-day period prior to Month 3), i.e., 43% of non-missing assessments for the primary analysis, consistent with the use of 3 days per week as the minimum number of completed diary entries as suggested in recent research ((Griffiths & al, 2018), (Cappelleri & Bushmakin, Biopharmaceutical Report, 2020), (Cappelleri & Bushmakin, Biopharmaceutical Report, 2020), (Cappelleri & Bushmakin, Biopharmaceutical Report, 2020), Cappelleri & Bushmakin, Biopharmaceutical Report, 2020), (Cappelleri & Bushmakin, Biopharmaceutical Report, 2020), completed daily eDiaries for DYS, NMPP and analgesic use.

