Mean pelvic pain scores for DYS and for NMPP for each subject will be calculated in the same way as for the primary endpoints. The change from baseline to Month 6 (the last 28 days of randomized treatment up to the Month 6 visit, defined as the last 28 days prior to and including the last treatment administration date as defined in Section 4.2.11, or the 28 calendar days immediately prior to and including the last dose date for subjects who discontinue treatment prior to Month 6) in DYS using the VRS, and the change from baseline to Month 6 (the last 28 days of randomized treatment up to the Month 6 visit, defined as the last 28 days of randomized treatment up to the Month 6 visit, defined as the last 28 days prior to and including last treatment administration date as defined in Section 4.2.11 or the 28 calendar days immediately prior to and including the last dose date for subjects who discontinue treatment administration date as defined in Section 4.2.11 or the 28 calendar days immediately prior to and including the last dose date for subjects who discontinue treatment prior to Month 6) in NMPP using the VRS, will be analyzed via analysis of covariance with treatment group as the main effect (three values) and including the baseline pain score as a covariate. The mean pelvic pain scores for DYS and NMPP and change from baseline will also be descriptively summarized.

SAS Code (may be updated at analysis stage to fit the data): Analysis of covariance

```
proc GLM data=dataset order=internal ;
    class treatment;
    model chg = base_pain treatment;
    lsmeans treatment / pdiff = control('1') cl alpha=0.05 at means
adjust=bon;
    ods output lsmeans = lsm diff=pvals lsmeancl=lsmeancl
lsmeandiffcl=lsmeandiffcl; * contains the adjusted means;
```

run;

CRS-BS-TP-000005 V 1.0

Page 66 of 127

Cytel Confidential: This is a controlled document and shall not be changed, saved, copied or reproduced by any unauthorized person.

Sponsor:	ObsEva		
Protocol:	18-OBE2109-003		
Document Version No.:	V5.0	Document Date:	13-JUN-2022

The number and percentage of subjects with a reduction of X from baseline to Month 6 for DYS, with a reduction of X from baseline to Month 6 for NMPP will be presented. The reduction will be defined in a similar way as for the primary endpoint, but for the Month 6 timepoint. The value for the threshold X will be obtained from the MCT analysis based on blinded Month 6 data (X can be different for DYS and NMPP).

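### A bleed that falls wholly in unanswered diary days can be scored as zero dysmenorrhea: the zero rule has no completeness condition, and 12 of 28 answered days suffice

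*SAP*

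**What the plan says.** Several rules in the SAP meet at this point.

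- **Days that count (4.6.2.1.1).** "DYS will use days with uterine bleeding, defined as those days on which the subject records any uterine bleeding or spotting". An unanswered day cannot contribute to DYS.
- **Zero rule (4.6.2.1.1).** With no recorded bleeding day, "then the mean score for DYS will be set equal to zero (which reflects the absence of any DYS during that reporting time period". Protocol 13.5.2 has the same rule. The stated trigger is that the mean has no value "because her daily eDiary reports indicate that she did not experience uterine bleeding on any days during the 28 calendar day period".
- **Minimum diary (4.6.2.1.2).** "The required minimum number of completed daily eDiary entries will be set to 12 days of each 28-day period". Below that, "Subjects who have less than the minimum number of days available will be excluded from the analysis". The reliance on observed days is justified so: "This effectively assumes that the individual values such as daily eDiary assessments (observed or not) are independent of being missing".
- **Response (4.6.1.3 and 4.6.2.1.1).** The pain threshold is "Dysmenorrhea (VRS): X=-1.10". Analgesic use must also not have increased, and for DYS it is averaged over the recorded bleeding days.
- **Month 6 (4.6.3.1).** "Mean pelvic pain scores for DYS and for NMPP for each subject will be calculated in the same way as for the primary endpoints". The rule therefore carries into the change in DYS at Month 6, the first ranked secondary endpoint.

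**The concern.** Nothing links the zero rule to the minimum-diary rule. The text does not separate a woman who reports no bleeding on 28 answered days from one who reports none on 12. If the second woman menstruated during her unanswered days, her DYS mean has no days to average and is set to 0, the best value on the 0-3 scale. Her change is then minus her whole baseline.

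The independence assumption does not cover this step. It can support letting the observed bleeding days stand for the unobserved ones. Here no bleeding day is observed, and an unseen bleed is replaced by the most favourable score.

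At stake is the validity of one co-primary endpoint, of DYS response at the other visits, and of the ranked endpoint that opens the fixed sequence. The last is a continuous change, so there the false zero enters directly, with no threshold or analgesic condition in between.

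**Working it through.** **1. The plan's own figure.** Inputs from SAP 4.1: 150 per group; two-sided alpha 0.05/2 = 0.025; DYS 14.6% on placebo against 48.6% (75 mg) or 64.7% (200 mg); NMPP 18.8% against 42.1%. With the two-proportion normal formula, power is above 99.9% for DYS at either dose. For NMPP, (0.233 − 2.241 × 0.0531)/0.0514 = 2.22, which gives 98.7%. Joint power is at least 98.7%, so the stated figure of more than 95% is reproduced.

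**2. Room for a hidden bleed.** 12/28 = 42.9%, so up to 28 − 12 = 16 days may be unanswered.

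**3. Chance that a whole bleed is hidden.** Bleed length b and the gap pattern are assumptions, since the documents give neither. With m unanswered days:

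- Missed at random: C(28 − b, m − b)/C(28, m).
- One unbroken gap, gap and bleed both placed uniformly inside the window: (m − b + 1)/(28 − b + 1). With circular placement the denominator is 28.

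| Unanswered days | Bleed | At random | One gap, inside window |
|---|---|---|---|
| 16 | 3 days | 17.1% | 53.8% |
| 16 | 5 days | 4.4% | 12/24 = 50.0% |
| 16 | 7 days | 1.0% | 45.5% |
| 7 | 3 days | 1.1% | 19.2% |
| 7 | 5 days | 0.02% | 3/24 = 12.5% |
| 7 | 7 days | about 0% | 4.5% |

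Circular placement gives 12/28 = 43% for the 16-day gap and 5-day bleed.

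**4. From zero score to response.** The pain criterion is met only if baseline DYS is at least 1.10. Inclusion criterion 6b(ii) allows less: two days scored 2 and three scored 0 average 4/5 = 0.8. The analgesic criterion must also be met, but its DYS average runs over recorded bleeding days. With none recorded it has no days, and the SAP gives no rule for that case.

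**5. Effect on the DYS comparison, 75 mg.** Let f be the share of true non-responders turned into responders, so a rate p becomes p + f(1 − p). The planned odds ratio is 5.53.

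- f = 5% in both arms: 18.9% against 51.2%, odds ratio 4.51, power above 99.9%.
- f = 10% in both arms: 23.1% against 53.7%, odds ratio 3.86, power above 99.9%.
- f = 10% on placebo only: 23.1% against 48.6%, power 99.3%. Joint power with NMPP is at least 0.993 + 0.987 − 1 = 98.0%.
- f = 15% on placebo only: 27.4% against 48.6%, power 94.3%.

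Reaching f = 10% needs 0.10/0.50 = 20% to 0.10/0.43 = 23% of placebo non-responders to have an unbroken 16-day gap, even if every hidden bleed became a response.

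**6. Opposite direction.** If no true effect exists (14.6% in both arms) and the error occurs only in an active arm, the chance of a false win on the DYS test is 3.3% at f = 2% and 10.5% at f = 5%, against a nominal 1.25%. A dose must also win on NMPP, so these are not trial-level error rates.

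**7. Other safeguards.** The 75% diary requirement (inclusion criterion 7) covers screening only. Recovery of a missed day from the next day's entry (SAP 4.2.8.3) is given for analgesics and study drug, not for bleeding or pain. SAP V2.0 removed diary compliance as a potential major deviation because the minimum-days rule already applies (SAP 5). None of the planned supportive analyses (Cochran-Mantel-Haenszel, non-endometriosis analgesics, Per Protocol, discontinuers as non-responders, reference-based imputation, analgesics over all days) varies the zero rule or the 12-day minimum.

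**The case against.** The strongest reply is textual. The zero applies when diary reports indicate no bleeding on any of the 28 days, and an unanswered day indicates nothing. Read strictly, a 12-day diary does not trigger the zero; DYS is then not assessable and the woman is a non-responder under SAP 4.2.8.1. This reading is possible, but no such condition is written, and the observed-data rule points the other way. The close of the minimum-days paragraph in SAP 4.6.2.1.2 is also garbled in the text available, so a further condition there cannot be excluded.

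The second reply is that long gaps should be rare: daily alarms, missed-entry emails, remote checks and visit checks are planned (Protocol 10.2 and 10.3.2). That stands, and the figure of 0.02% for 7 days missed at random shows how far good completion removes the problem. It does not remove long gaps, and the SAP itself records eDiary technical problems during screening and a change of device vendor (4.2.8.3 and 4.2.10).

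Third, some visibility exists already. Bleeding days are analysed by arm and visit (4.6.4.16), derived data are listed, and overall pelvic pain at Month 6 is a ranked endpoint free of this rule. None of these shows how many DYS zeros rest on incomplete diaries.

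A reader might infer that placebo response is inflated by several percentage points. The documents give no share of women with such gaps, so no such figure can be supported. A reader might also infer that each hidden bleed creates a responder; step 4 shows that it need not.

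**Conclusion.** The gap in the rules is real: as written, they permit a hidden bleed to score as zero DYS on a co-primary endpoint and on the first ranked secondary endpoint. Its frequency cannot be derived from the documents. The conditional chances, 0.02% to about 50% for a 5-day bleed, depend on assumed bleed length, number of missed days and gap pattern.

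Dilution is the likely effect, because only women who still bleed can have a hidden bleed, and these are plausibly more common on placebo. The direction is not guaranteed; it would reverse if missed bleeds were concentrated in an active arm, for which the documents give no evidence. A reader might infer that the trial is underpowered. Step 5 does not support that: even 10% misclassification confined to placebo leaves joint power near 98%. This is a matter of endpoint validity and of an unclear derivation rule, not a sample-size error.

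**What to change.** 1. **If the definition can still be changed blind to treatment.** State in SAP 4.6.2.1.1, and so for 4.6.3.1, that the zero applies only when the answered bleeding items are enough to show that no bleed occurred. Use a completeness or maximum-gap rule chosen without knowledge of treatment. Otherwise DYS is not assessable: non-responder, and zero change for the numeric endpoint, as in Protocol 13.5.8 and SAP 4.2.8.1 and 4.6.2.1.2. State also how the analgesic criterion is judged when no bleeding day is recorded.
2. **If the primary definition is fixed or data are unblinded.** This may apply: SAP 4.3 allows results to reach the sponsor once the Month 6 thresholds are in the SAP, and they entered at V4.0. Leave the primary definition unchanged. Add a sensitivity analysis of co-primary DYS and of the first ranked endpoint that treats zeros from incomplete diaries as not assessable. Report zero-rule cases by arm and by number of days answered.

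The cost is a paragraph of SAP text, one derivation flag and one table, all from data already collected. The drawback is that some truly amenorrheic women with incomplete diaries, plausibly more of them on active drug, lose a DYS response wherever the stricter rule is applied. Any cut-off for gap length is partly arbitrary, so the by-arm counts should accompany the result.
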